3.3.1.3.1 Gastrointestinal Disorders

The most common GI AEs reported in clinical studies with cabozantinib are diarrhea, oral pain, dyspepsia, stomatitis, and dysphagia.

Diarrhea

Subjects should be instructed to notify their physician immediately at the first signs of poorly formed or loose stool or an increased frequency of bowel movements. Administration of antidiarrheal/antimotility agents is recommended at the first sign of diarrhea as initial management. Some subjects may require concomitant treatment with more than one antidiarrheal agent. When therapy with antidiarrheal agents does not control the diarrhea to tolerable levels, study treatment should be temporarily interrupted or dose reduced per Table 3-2 and Table 3-3.

In addition, general supportive measures should be implemented including continuous oral hydration, correction of fluid and electrolyte abnormalities, small frequent meals, and stopping lactose-containing products, high fat meals, and alcohol.

Nausea and Vomiting

Antiemetic agents are recommended as clinically appropriate at the first sign of nausea and vomiting or as prophylaxis to prevent emesis, along with supportive care in accordance to clinical practice guidelines^{30,31}. The 5-HT3 receptor antagonists are recommended over chronic use of NK-1 receptor antagonists and dexamethasone (NK-1 receptor antagonists can induce or inhibit CYP3A4, and glucocorticoids induce CYP3A4 and thus could lower cabozantinib exposure (see Sections 3.4.4). Caution is also recommended with the use of nabilone, which is a weak inhibitor of CYP3A4. When therapy with antiemetic agents does not control the nausea or vomiting to tolerable levels, study treatment should be temporarily interrupted or dose reduced per Table 3-2 and Table 3-3.

Stomatitis and Mucositis

Preventive measures include a comprehensive dental examination to identify any potential complications before study treatment is initiated. Removal of local factors should be instituted as indicated, such as modification of ill-fitting dentures and appropriate care of gingivitis.

During treatment with cabozantinib good oral hygiene and standard local treatments such as nontraumatic cleansing and oral rinses (eg, with a weak solution of salt and baking soda) should be maintained. The oral cavity should be rinsed after meals, and dentures should be cleaned and brushed often to remove plaque. Local treatment should be instituted at the earliest onset of symptoms. Obtain bacterial/viral culture if oral infection is suspected and treat infection as indicated by local guidelines. When stomatitis interferes with adequate nutrition and local therapy is not adequately effective, dose reduction or temporary withholding of cabozantinib should be considered per Table 3-2 and Table 3-3.

3.3.1.4 Hepatobiliary Disorders

Elevations of transaminases have also been observed during treatment with cabozantinib. In general, it is recommended that subjects with elevation of ALT, AST, and/or bilirubin have more frequent laboratory monitoring of these parameters. Other causes that may contribute to transaminase elevations should be considered. If possible, hepatotoxic concomitant medications and alcohol should be discontinued in subjects who develop elevated transaminases.

Because subjects may enter the study with elevations of AST/ALT at baseline, the following guidelines in Table 3-5 should be used for dose modifications:

 Table 3-5:
 Management of Transaminase Elevation

Transaminase elevation CTCAE v4.0	Intervention
Subjects with AST and AI	LT less than or equal to the ULN at baseline
Grade 1	Continue cabozantinib with weekly monitoring of liver function tests (LFTs) for at least 4 weeks. Then resume the standard protocol-defined monitoring of liver function tests (LFTs).
Grade 2	Continue cabozantinib with at least twice weekly monitoring of LFTs for 2 weeks. Then weekly for 4 weeks. If LFTs continue to rise within Grade 2, interrupt cabozantinib treatment. Then continue with at least weekly LFTs until resolution to Grade ≤ 1 . Study treatment may then be resumed at a one-dose-level reduction of cabozantinib
Grade 3	Interrupt cabozantinib treatment and monitor with at least twice weekly LFTs until Grade ≤ 2 . Then continue with at least weekly LFTs until resolution to Grade ≤ 1 . Cabozantinib may then be resumed at a one-dose-level reduction.
Grade 4	Discontinue study treatment permanently. LFTs should be monitored as clinically indicated, at least 2 to 3 times per week, until resolution to Grade ≤ 1. If the subject was unequivocally deriving clinical benefit, the subject may be able to resume treatment at a lower dose of cabozantinib as determined by the investigator and MD Anderson Cancer Center/IND Office but only with MD Anderson Cancer Center/IND Office approval.
Subjects with AST or ALT	Tabove the ULN but ≤ 3.0 x ULN (ie, Grade 1) at baseline
≥ 1.5 fold increase of AST or ALT AND both AST and ALT are ≤ 5.0 x ULN	Continue cabozantinib treatment with at least twice weekly monitoring of LFTs for 4 weeks and weekly for 4 weeks. If LFTs continue to rise, interrupt study treatment. Then continue with at least weekly LFTs until resolution to Grade ≤ 1. Study treatment may then be resumed at a one-dose-level reduction of cabozantinib
≥ 1.5 fold increase of AST or ALT and at least one of AST or ALT is Grade 3 (ie, AST or ALT > 5.0 but ≤ 20.0 x ULN)	Interrupt study treatment and monitor with at least twice weekly LFTs until Grade \leq 2. Then continue with at least weekly LFTs until resolution to Grade \leq 1. Study treatment may then be resumed at a one-dose-level reduction of cabozantinib.
Grade 4	Discontinue study treatment permanently. LFTs should be monitored as clinically indicated, at least 2 to 3 times per week, until resolution to Grade ≤ 1. If the subject was unequivocally deriving clinical benefit, the subject may be able to resume treatment at a lower dose as determined by the investigator and MD A nderson Cancer Center/IND Office , but only with MD Anderson Cancer Center/IND Office approval.

Cabozantinib treatment should also be interrupted when AST or ALT increases are accompanied by progressive elevations of total bilirubin, and/or elevations of coagulation tests (eg, International Normalized Ratio [INR]). Monitoring of transaminases should be intensified (2–3 times per week) and cabozantinib should be held until the etiology of the abnormalities is determined and these abnormalities are corrected or stabilize at clinically acceptable levels (INR $< 1.5 \times \text{upper limit of normal [ULN]}$, total bilirubin $< 1.5 \times \text{ULN}$, aminotransferases \le baseline grade).

Subjects must have cabozantinib permanently discontinued if transaminase elevations are accompanied by evidence of impaired hepatic function (bilirubin elevation $> 2 \times ULN$), in the absence of evidence of biliary obstruction (ie, significant elevation of alkaline phosphatase) or some other explanation of the injury (eg, viral hepatitis, alcohol hepatitis), because the combined finding (ie, Hy's Law cases) represents a signal of a potential for the drug to cause severe liver injury.

All subjects who develop isolated bilirubin elevations of Grade 3 should have study treatment held until recovered to Grade ≤ 1 or baseline (or lower). If this occurs within 6 weeks of the dosing delay, study treatment may continue at a reduced dose. In subjects without biliary obstruction and Grade 4 bilirubin elevation, or with recurrence of Grade 3 bilirubin elevation after a dose reduction, study treatment must be permanently discontinued.

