3.3 Cabozantinib Dose Modifications, Interruptions, and Discontinuation

Subjects will be monitored for AEs from the time of signing informed consent through 30 days after the date of the decision to permanently discontinue cabozantinib treatment. Subjects will be instructed to notify their physician immediately at the onset of any AE. Causality assessment of AEs should include at minimum confounding factors such as

disease and concomitant medications. AE severity will be graded by the investigator in accordance with CTCAE v.4.0.

The following should be taken into consideration in decisions regarding dose modifications (reductions or interruption):

- As a general approach all AEs should be managed with supportive care at the earliest signs of toxicity considered related to the study treatment. Should this be ineffective, dose interruptions and/or reductions should be considered to prevent worsening of toxicity.
- Dose modification criteria for cabozantinib are detailed in Section 3.3. Dose interruptions and/or reductions should be implemented for unacceptable toxicity. Doses may be modified at any time while on study.
- The assigned dose for cabozantinib is 60 mg/day. 20 mg dose reduction levels of cabozantinib are permitted (see Table 3-2).
- Dose reductions or interruptions may also occur in the setting of lower grade toxicity than defined in Sections 3.3.1 and 3.3.1.3, if the investigator feels it is in the interest of a subject's safety and will optimize drug tolerability.
- Interruption of cabozantinib treatment for AEs may occur at any time per investigator discretion. If treatment is interrupted due to AEs for more than 6 weeks, cabozantinib should be discontinued unless there is unequivocal evidence that the subject is benefitting. In this situation, a subject may be able to restart therapy with a dose reduction upon resolution of the toxicity.
- Dose interruptions for reason(s) other than AEs (eg, surgical procedures) can be longer than 6 weeks per the discretion of the investigator.

Guidelines for the management of specific AEs are provided in Section 3.3.1.3.

Table 3-2: Dose Reductions of Cabozantinib

Assigned dose	First Dose Level Reduction	Second Dose Level Reduction
60-mg cabozantinib oral qd	40-mg cabozantinib oral qd	20-mg cabozantinib oral qd

qd= once daily

Cabozantinib should be discontinued if a qd dose of 20-mg cabozantinib (minimum dose) is not tolerated

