4 STUDY POPULATION

4.1 Inclusion Criteria

Malignant PH and PG patients will be eligible for enrollment as defined by the inclusion and exclusion criteria as follows:

- 1. 18 years of age or older
- 2. Histological confirmation of PH/PG
- 3. Locally advanced or metastatic disease not amenable to surgery
- 4. Patients enrolled in the main branch should have measurable disease. Patients with a predominance of bone disease who have small, non-measurable or small measurable lesions other than bone, may be included per the Principal

- Investigator's discretion, in the exploratory branch of the study for patients with bone metastases only.
- 5. Progressive disease per RECIST 1.1 as determined by the investigator within the 12 months preceding study enrollment
- 6. Assessment of all known disease sites, eg, by computerized tomography (CT) scan, magnetic resonance imaging (MRI), bone scan as appropriate, and/or FDG-PET scan within 28 days before the first dose of cabozantinib
- 7. Eastern Cooperative Oncology Group (ECOG) performance status of ≤ 2 .
- 8. Life expectancy of at least 3 months
- 9. Organ and marrow function and laboratory values as follows within 4 days prior to the first dose of cabozantinib:
 - a. Absolute neutrophil count (ANC) $\geq 1500/\text{mm}^3$ without colony stimulating factor support
 - b. Platelets $\geq 100,000/\text{mm}^3$
 - c. Hemoglobin $\geq 9 \text{ g/dL}$
 - d. Bilirubin $\leq 1.5 \times$ the upper limit of normal (ULN). For subjects with known Gilbert's disease, bilirubin $\leq 3.0 \text{ mg/dL}$
 - e. Serum albumin $\geq 2.8 \text{ g/dl}$
 - f. Serum creatinine $\leq 1.5 \times ULN$ or creatinine clearance (CrCl) ≥ 50 mL/min. For creatinine clearance estimation, the Cockcroft and Gault equation should be used:

Male: $CrCl (mL/min) = (140 - age) \times wt (kg) / (serum creatinine \times 72)$ Female: Multiply above result by 0.85

- g. Alanine aminotransferase (ALT) and aspartate aminotransferase (AST) $\leq 3.0 \times \text{ULN}$
- h. Lipase < 2.0 x the upper limit of normal and no radiologic or clinical evidence of pancreatitis
- i. Urine protein/creatinine ratio (UPCR) ≤ 1
- j. Serum phosphorus, calcium, potassium \geq LLN and magnesium \geq 1.2 mg/dL
- 10. Capable of understanding and complying with the protocol requirements and has signed the informed consent document.

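### Low-priority safety wording: Section 3.3.1.4 lets raised total alkaline phosphatase stand as evidence of biliary obstruction, so, read literally, a bone-derived rise can lift the permanent Hy's Law stop

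*Combined protocol and SAP*

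**What the plan says.** Section 3.3.1.4 (Hepatobiliary Disorders) has several layers.

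- **Permanent stop.** Raised transaminases with bilirubin above 2 x ULN require permanent discontinuation, "in the absence of evidence of biliary obstruction (ie, significant elevation of alkaline phosphatase) or some other explanation of the injury". The section gives its reason: the combined finding signals a potential for severe drug-induced liver injury.
- **Hold.** When AST or ALT rises together with progressive bilirubin or coagulation abnormalities, "cabozantinib should be held until the etiology of the abnormalities is determined and these abnormalities are corrected or stabilize at clinically acceptable levels". The stated levels are INR and total bilirubin each below 1.5 x ULN, and aminotransferases no worse than baseline grade.
- **Table 3-5, Grade 3 transaminases.** Interrupt, monitor to Grade 1 or lower, and then: "Cabozantinib may then be resumed at a one-dose-level reduction". This row does not ask for IND Office approval. The Grade 4 rows do.
- **Grade 4 bilirubin.** A further permanent stop begins: "In subjects without biliary obstruction and Grade 4 bilirubin elevation". Here obstruction is named without the ALP gloss.

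Section 3.3 adds a general limit: "If treatment is interrupted due to AEs for more than 6 weeks, cabozantinib should be discontinued unless there is unequivocal evidence" of benefit. It also asks for disease to be weighed in causality: "Causality assessment of AEs should include at minimum confounding factors such as" disease and concomitant medications.

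**The concern.** The permanent stop takes rechallenge out of the investigator's hands when drug-induced liver injury is a live possibility. Its exemption rests on total ALP, with no threshold, no comparison with the patient's own baseline, and no requirement that the enzyme come from the biliary tract. This protocol itself treats ALP as a bone marker, and many of its patients will have bone metastases. If ALP is already high from bone, the literal wording lets an unrelated laboratory value excuse a true drug-injury case from the mandatory stop and leaves rechallenge open.

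**Working it through.** The plan gives no figure to reproduce on this point. The check is a reading of the rules, plus a count of patients with bone metastases.

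**1. Is the parenthesis a definition or an example?** The same sentence uses *ie* for ALP and *eg* for viral and alcohol hepatitis. Table 3-5 also uses *ie* to define (Grade 3 as AST or ALT above 5.0 and up to 20.0 x ULN). The literal reading is therefore a definition.

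**2. Can total ALP come from bone in this protocol's own terms?** Yes. Sections 1.1.1.5 and 1.1.1.6 describe prostate-cancer patients with bone metastases and elevated total ALP at baseline, and link total ALP to osteoblast activity. Section 2.1 lists bone-specific ALP as a turnover marker.

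**3. Would entry limits or scheduled tests separate the sources?**

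- Section 4.1, criterion 9 ("Organ and marrow function and laboratory values as follows within 4 days prior to the first dose of cabozantinib") has items a to j, which is 10 items. None limits ALP.
- Table 5-1 footnote 1 and the Section 5.4 panels both list total ALP. Neither lists GGT or bone-specific ALP.
- Total ALP is measured at screening and again within 4 days before the first dose, so each patient's own baseline is known.

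**4. Trace one case.** Take a patient with bone metastases and normal AST and ALT at baseline. On 60 mg, transaminases reach Grade 3, bilirubin is above 2 x ULN but below Grade 4, and ALP is raised from bone.

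| Rule | Effect in this case |
|---|---|
| Permanent stop | Lifted if raised ALP counts as obstruction |
| Hold until cause and values are settled | Applies |
| Grade 4 transaminase row | Not reached |
| Grade 4 bilirubin stop | Not reached |
| Isolated Grade 3 bilirubin rule | Does not fit, because the rise is not isolated |
| 6-week limit | Bites only if the interruption exceeds 6 weeks |
| Table 3-5, Grade 3 row | Permits resumption at 40 mg (Table 3-2), with no IND Office approval asked for |

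The hold asks for a cause, but the next paragraph offers one: raised ALP equals obstruction. Recovery while off drug does not settle the matter, because a true drug injury could also recover when the drug is withheld.

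**5. How many patients have bone metastases?** This is a proxy only.

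- By design: 8 / 22 = 36%.
- From the 40/40/20 split in Section 1.3.1, assuming visceral disease is measurable and enrolment follows the split: main-branch share with bone = 0.40 / (0.40 + 0.40) = 0.50; 14 x 0.50 = 7; (8 + 7) / 22 = 15 / 22 = 68%.
- From Section 1.1 (skeleton involved in 80%, and 20% of these bone-only): both sites = 0.80 x 0.80 = 0.64; main-branch share = 0.64 / (0.64 + 0.20) = 0.762; 14 x 0.762 = 10.7; (8 + 10.7) / 22 = 85%.

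These figures count bone metastases. The documents give no rate of raised ALP in this disease and no probability of a combined transaminase and bilirubin rise, so the number who would meet the gap cannot be calculated.

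**The case against.** The strongest reply is that the parenthesis should not be read apart from its sentence. The words about some other explanation of the injury imply that obstruction must itself explain the injury, and ALP known to come from bone explains neither raised transaminases nor raised bilirubin. The Grade 4 bilirubin rule names obstruction with no mention of ALP, which suggests that obstruction is the concept and ALP only its sign. Before any restart, the investigator must establish the cause, consider other contributors, weigh disease in the causality assessment and see the values settle. Resumption is optional and at a lower dose. Section 5.2 calls for more frequent assessments when clinically indicated, so the short routine panel does not prevent a proper work-up. In the prostate-cancer data that the protocol cites, total ALP fell on cabozantinib in most patients with bone metastases and a raised baseline.

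Much of this stands, and it is why the point is low priority. It does not remove the point, because no sentence overrides the literal *ie*.

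A reader might infer more than the documents support:

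- **That the exemption removes liver protection altogether.** It lifts only the permanent stop. The hold, the Grade 4 rules and the 6-week limit remain.
- **That the plan requires rechallenge.** It only permits it.
- **That 36% to 85% of patients are exposed.** Those are shares with bone metastases, not with raised ALP, and still less with raised ALP at the time of a combined liver signal.
- **That the ALP gloss also weakens the Grade 4 bilirubin stop.** That rule does not contain it.

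**Conclusion.** The point holds as a low-priority safety wording fix. A stated stopping rule can misfire in patients with bone metastases if the ALP parenthesis is taken at its word. The gap is mainly Grade 3 transaminases with bilirubin above 2 x ULN but below Grade 4, settling within 6 weeks, in a patient whose ALP is raised from bone. The number affected is unknown and likely very small, possibly none. The conclusion assumes that an investigator applies the parenthesis literally and then chooses to resume; a careful one may do neither. Section 7 states that there is no formal toxicity monitoring rule, so stopping rules for individual patients carry more of the protection. No endpoint, sample-size statement or analysis is affected.

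**What to change.** In the permanent-stop sentence of Section 3.3.1.4, change *ie* to *eg*, and add:

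> In a patient with bone metastases or with ALP above ULN at baseline, raised total ALP alone is not evidence of biliary obstruction; the exemption requires ALP to have risen above the patient's own pre-dose value together with other clinical, laboratory or imaging evidence of obstruction found in the etiology work-up already required.

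Leave the bilirubin trigger of 2 x ULN as it is.

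The cost is one changed word and one added sentence. Pre-dose and on-treatment ALP are already collected, and no scheduled test is added. The downside is that a few more cases may reach the mandatory stop, including some in which obstruction is real but not shown. The wording still leaves judgement about what counts as other evidence, but raised ALP by itself no longer suffices in these patients.

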3.3.1.5 Fatigue, Anorexia, and Weight Loss

Fatigue has been reported during treatment with cabozantinib. Common causes of fatigue such as anemia, deconditioning, emotional distress (depression and/or anxiety), nutrition, sleep disturbance, and hypothyroidism should be ruled out and/or these causes treated in accordance to standard of care. Individual non-pharmacological and/or pharmacologic interventions directed to the contributing and treatable factors should be given. Pharmacological management with psychostimulants such as methylphenidate should be considered after disease specific morbidities have been excluded. Note: Chronic use of modafinil should be avoided because of its potential to reduce cabozantinib exposure (see Investigator's Brochure). Refer to Table 3-3 for general management guidelines.

Anorexia and weight loss should be managed in accordance to local standard of care including nutritional support. Pharmacologic therapy such as megestrol acetate should be considered for appetite enhancement. If fatigue, anorexia, or weight loss cannot be adequately managed, study treatment should be temporarily interrupted or dose reduced per Table 3-2 and Table 3-3.

3.3.1.6 Skin Disorders

Palmar-plantar erythrodysesthesia syndrome (also known as hand-foot syndrome), skin rash (including blisters, erythematous rash, macular rash, skin exfoliation, dermatitis acneiform, and papular rash), pruritus, dry skin, and erythema have been reported in cabozantinib-treated subjects. All subjects on study should be advised on prophylactic skin care. This includes the use of hypoallergenic moisturizing creams, ointment for dry skin, and sunscreen with sun protection factor ≥ 30 , avoidance of exposure of hands and feet to hot water, protection of pressure-sensitive areas of hands and feet, and use of thick cotton gloves and socks to prevent injury and to keep the palms and soles dry. Subjects with skin disorders should be carefully monitored for signs of infection (eg, abscess, cellulitis, or impetigo).

Early signs of hand-foot syndrome could be tingling, numbness, and slight redness or mild hyperkeratosis. Early manifestations include painful, symmetrical red and swollen areas on the palms and soles. The lateral sides of the fingers or peri-ungual zones may also be affected. Adequate interventions are required to prevent worsening of skin symptoms such as blisters, desquamations, ulcerations, or necrosis of affected areas. Aggressive management of symptoms is recommended, including early dermatology referral. Treatment guidelines for PPE related to study treatment are presented in Table 3-6.

In the case of study treatment-related skin changes (eg, rash, hand-foot syndrome), the investigator may request that additional assessments be conducted with the subject's consent. These assessments may include digital photographs of the skin changes and/or a biopsy of the affected skin and may be repeated until the skin changes resolve.

 Table 3-6:
 Management of Treatment-emergent PPE Syndrome

Hand-Foot Skin F	Hand-Foot Skin Reaction and Hand Foot Syndrome (PPE)	
Grade 1	Continue cabozantinib at current dose. Start urea 20% cream twice daily and clobetasol 0.05% cream once daily. Assess subject at least weekly for changes in severity. Subjects should be instructed to notify investigator immediately if severity worsens.	
Grade 2	If tolerable, continue cabozantinib at current dose.	
	If intolerable, reduce cabozantinib dose to next lower level and/or interrupt dosing. Start/continue urea 20% cream twice daily and clobetasol 0.05% cream once daily. Add analgesics for pain control with NSAIDs/GABA agonists/narcotics if needed. Assess subject at least weekly for changes in severity. If treatment was interrupted (but not reduced), treatment may be restarted at the same dose or at one dose level lower when reaction decreases to Grade 1 or 0. If a treatment interruption is again required, the dose must be reduced when treatment resumes.	
	Subjects should be instructed to notify investigator immediately if severity worsens. If severity worsens at any time, or affects self-care, proceed to the management guidelines for Grade 3 PPE.	
Grade 3	Interrupt study treatment until severity decreases to Grade 1 or 0. Start/continue urea 20% cream twice daily and clobetasol 0.05% cream once daily. Pain control with NSAIDs/GABA agonists/narcotics. Treatment may restart at one dose level lower when reaction decreases to Grade 1 or 0. Permanently discontinue subject from study if reactions worsen or do not improve within 6 weeks.	

GABA, γ-aminobutyric acid; NSAID, nonsteroidal anti-inflammatory drugs; PPE, palmar-plantar erythrodysesthesia

